8. DATA MANAGEMENT

- For this study (1-eDM) subject data will be entered into GSK defined CRFs, transmitted electronically to GSK.
- Management of clinical data will be performed in accordance with applicable GSK standards and data cleaning procedures to ensure the integrity of the data, e.g., removing errors and inconsistencies in the data.
- Adverse events and concomitant medications terms will be coded using MedDRA (Medical Dictionary for Regulatory Activities) and an internal validated medication dictionary, GSKDrug.

9. STATISTICAL CONSIDERATIONS AND DATA ANALYSES

No statistical analysis will be conducted for this study. Reported data will be summarized.

9.1. Interim Analysis

When required, an interim analysis will be performed in order to provide open-label safety data to inform the risk-benefit assessment of mepolizumab in EGPA.

10. STUDY GOVERNANCE CONSIDERATIONS

10.1. Regulatory and Ethical Considerations, Including the Informed Consent Process

Prior to initiation of a site, GSK will obtain favourable opinion/approval from the appropriate regulatory agency to conduct the study in accordance with ICH Good Clinical Practice (GCP) and applicable country-specific regulatory requirements.

The study will be conducted in accordance with all applicable regulatory requirements, and with GSK policy.

The study will also be conducted in accordance with ICH Good Clinical Practice (GCP), all applicable subject privacy requirements, and the guiding principles of the current version of the Declaration of Helsinki. This includes, but is not limited to, the following:

- IRB/IEC review and favourable opinion/approval of the study protocol and amendments as applicable
- Signed informed consent to be obtained for each subject before participation in the study (and for amendments as applicable)
- Investigator reporting requirements (e.g. reporting of AEs/SAEs/protocol deviations to IRB/IEC)
- GSK will provide full details of the above procedures, either verbally, in writing, or both.

- Signed informed consent must be obtained for each subject prior to participation in the study
- The IEC/IRB, and where applicable the regulatory authority, approve the clinical protocol and all optional assessments, including genetic research.
- Optional assessments (including those in a separate protocol and/or under separate informed consent) and the clinical protocol should be concurrently submitted for approval unless regulation requires separate submission.
- Approval of the optional assessments may occur after approval is granted for the clinical protocol where required by regulatory authorities. In this situation, written approval of the clinical protocol should state that approval of optional assessments is being deferred and the study, with the exception of the optional assessments, can be initiated.

10.2. Quality Control (Study Monitoring)

- In accordance with applicable regulations including GCP, and GSK procedures, GSK monitors will contact the site prior to the start of the study to review with the site staff the protocol, study requirements, and their responsibilities to satisfy regulatory, ethical, and GSK requirements.
- When reviewing data collection procedures, the discussion will also include identification, agreement and documentation of data items for which the CRF will serve as the source document.

GSK will monitor the study and site activity to verify that the:

- Data are authentic, accurate, and complete.
- Safety and rights of subjects are being protected.
- Study is conducted in accordance with the currently approved protocol and any other study agreements, GCP, and all applicable regulatory requirements.

The investigator and the head of the medical institution (where applicable) agrees to allow the monitor direct access to all relevant documents

10.3. Quality Assurance

- To ensure compliance with GCP and all applicable regulatory requirements, GSK may conduct a quality assurance assessment and/or audit of the site records, and the regulatory agencies may conduct a regulatory inspection at any time during or after completion of the study.
- In the event of an assessment, audit or inspection, the investigator (and institution) must agree to grant the advisor(s), auditor(s) and inspector(s) direct access to all relevant documents and to allocate their time and the time of their staff to discuss the conduct of the study, any findings/relevant issues and to implement any corrective and/or preventative actions to address any findings/issues identified.

10.4. Study and Site Closure

- Upon completion or premature discontinuation of the study, the GSK monitor will conduct site closure activities with the investigator or site staff, as appropriate, in accordance with applicable regulations including GCP, and GSK Standard Operating Procedures.
- GSK reserves the right to temporarily suspend or prematurely discontinue this study at any time for reasons including, but not limited to, safety or ethical issues or severe non-compliance. For information studies, this can occur at one or more or at all sites.
- If GSK determines such action is needed, GSK will discuss the reasons for taking such action with the investigator or the head of the medical institution (where applicable). When feasible, GSK will provide advance notification to the investigator or the head of the medical institution, where applicable, of the impending action.
- If the study is suspended or prematurely discontinued for safety reasons, GSK will promptly inform all investigators, heads of the medical institutions (where applicable) and/or institution(s) conducting the study. GSK will also promptly inform the relevant regulatory authorities of the suspension or premature discontinuation of the study and the reason(s) for the action.
- If required by applicable regulations, the investigator or the head of the medical institution (where applicable) must inform the IRB/IEC promptly and provide the reason for the suspension or premature discontinuation.

10.5. Records Retention

- Following closure of the study, the investigator or the head of the medical institution (where applicable) must maintain all site study records (except for those required by local regulations to be maintained elsewhere), in a safe and secure location.
- The records must be maintained to allow easy and timely retrieval, when needed (e.g., for a GSK audit or regulatory inspection) and must be available for review in conjunction with assessment of the facility, supporting systems, and relevant site staff.
- Where permitted by local laws/regulations or institutional policy, some or all of these records can be maintained in a format other than hard copy (e.g., microfiche, scanned, electronic); however, caution needs to be exercised before such action is taken.
- The investigator must ensure that all reproductions are legible and are a true and accurate copy of the original and meet accessibility and retrieval standards, including re-generating a hard copy, if required. Furthermore, the investigator must ensure there is an acceptable back-up of these reproductions and that an acceptable quality control process exists for making these reproductions.
- GSK will inform the investigator of the time period for retaining these records to comply with all applicable regulatory requirements. The minimum retention time will meet the strictest standard applicable to that site for the study, as dictated by any

institutional requirements or local laws or regulations, GSK standards/procedures, and/or institutional requirements.

- The investigator must notify GSK of any changes in the archival arrangements, including, but not limited to, archival at an off-site facility or transfer of ownership of the records in the event the investigator is no longer associated with the site.

10.6. Provision of Study Results to Investigators, Posting of Information on Publically Available Clinical Trials Registers and Publication

Where required by applicable regulatory requirements, an investigator signatory will be identified for the approval of the clinical study report. The investigator will be provided reasonable access to statistical tables, figures, and relevant reports and will have the opportunity to review the complete study results at a GSK site or other mutually-agreeable location.

GSK will also provide the investigator with the full summary of the study results. The investigator is encouraged to share the summary results with the study subjects, as appropriate.

The procedures and timing for public disclosure of the results summary and for development of a manuscript for publication will be in accordance with GSK Policy.

10.7. Review Committees

An IDMC will be utilized until completion of the lead study MEA115921; their primary focus will be the monitoring of cardiovascular safety and all cause mortality.

12. APPENDICES

12.1. Appendix 1 – Abbreviations and Trademarks

Abbreviations

ADA	Anti-drug antibody
AE	Adverse Event
ALT	Alanine transaminase
CRF	Case Report Form
CV	Cardiovascular
DCSI	Developmental Core Safety Information
ECG	Electrocardiogram
EGPA	Eosinophilic Granulomatosis with Polyangiitis
FCBP	Female of childbearing potential
GCP	Good Clinical Practice
GSK	GlaxoSmithKline
HRT	Hormone replacement therapy
IB	Investigator's Brochure
ICH	International Conference on Harmonisation
IDMC	Independent data monitoring committee
IEC	Independent Ethics Committee
IL	Interleukin
IRB	Institutional review Board
IUD	Intrauterine device
IV	Intravenous(ly)
kg	kilogram
LAP	Long-term Access Programme
mAb	Monoclonal antibody
MedDRA	Medical Dictionary for Regulatory Activities
mg	milligrams
MSDS	Material Safety Data Sheet
NAB	Neutralizing antibodies
SAE	Serious Adverse Event
SC	Subcutaneous(ly)
SOC	System organ class
SRM	Study reference manual
SRT	Safety review team
ULN	Upper limit of normal
UK	United Kingdom

Trademark Information

Trademarks of the GlaxoSmithKline group of companies	Trademarks not owned by the GlaxoSmithKline group of companies
NONE	None

12.2. Appendix 2 – Anaphylaxis Criteria

Hypersensitivity reactions will be monitored using the diagnostic criteria for anaphylaxis as outlined by the Joint NIAID/FAAN Second Symposium on Anaphylaxis [Sampson, 2006]. The criteria do not make a distinction based on underlying mechanism. These criteria are summarized as follows:

- 4) Acute onset of an illness (minutes to several hours) with involvement of the skin, mucosal tissue, or both (e.g., generalized hives, pruritus or flushing, swollen lips-tongue-uvula), and at least one of the following:
 - c) Respiratory compromise (e.g., dyspnea, wheeze-bronchospasm, stridor, reduced PEF, hypoxemia)
 - d) Reduced BP or associated symptoms of end-organ dysfunction (e.g., hypotonia [collapse], syncope, incontinence)
- 5) Two or more of the following that occur rapidly after exposure to a likely allergen for that patient (minutes to several hours):
 - e) Involvement of the skin-mucosal tissue (e.g., generalized hives, itch-flush, swollen lips-tongue-uvula)
 - f) Respiratory compromise (e.g., dyspnea, wheeze-bronchospasm, stridor, reduced PEF, hypoxemia)
 - g) Reduced BP or associated symptoms (e.g., hypotonia [collapse], syncope, incontinence)
 - h) Persistent gastrointestinal symptoms (e.g., crampy abdominal pain, vomiting)
- 6) Reduced BP after exposure to known allergen for that patient (minutes to several hours):
 - c) Infants and children: low systolic BP (age specific) or greater than 30% decrease in systolic BP
 - d) Adults: systolic BP of less than 90 mm Hg or greater than 30% decrease from that person's baseline

12.3. Appendix 3 – Acceptable Birth Control

To be eligible for entry into the study, females of childbearing potential (FCBP) must commit to consistent and correct use of an acceptable method of birth control from the time of consent, for the duration of the trial, and for 4 months after the last mepolizumab administration.

- Male partner who is sterile prior to the female subject's entry into the study and is the sole sexual partner for that female subject
- Abstinence from penile-vaginal intercourse.
- UK only clarification: True abstinence from penile-vaginal intercourse when this is in line with the preferred and usual lifestyle of the subject.
- Implants of levonorgestrel or etonogestrel
- Injectable progestogen
- Oral contraceptive (either combined or progestogen alone)
- Estrogenic vaginal ring
- Percutaneous contraceptive patches
- Any intrauterine device (IUD) with a documented failure rate of less than 1% per year.
- Male condom combined with a vaginal spermicide (foam, gel, film, cream, or suppository)
- Male condom combined with a female diaphragm, either with or without a vaginal spermicide (foam, gel, film, cream, or suppository)

Females of childbearing potential are defined as females with functioning ovaries (i.e., post-menarche, premenopausal women with no documented impairment of oviductal or uterine function that would cause sterility). This category includes females with oligomenorrhea, females who are peri-menopausal, and young females who have begun to menstruate (adolescents). The information on the lack of impairment of oviductal or uterine function that would cause sterility can come from the site personnel's:

- Review of subject's medical records
- Medical examination of the subject
- Interview with the subject on her medical history.

Females of non-childbearing potential are defined as females with functioning ovaries and with a documented tubal ligation or hysterectomy; or females who are postmenopausal defined as 12 months of spontaneous amenorrhea with an appropriate clinical profile, e.g. age appropriate, >45 years, in the absence of hormone replacement therapy (HRT).

In questionable cases a blood sample for follicle stimulating hormone (FSH) and estradiol will be obtained and informat to confirm childbearing potential.

Females on HRT and whose menopausal status is in doubt will be required to use one of the contraception methods listed above for females of childbearing potential if they wish to continue their HRT during the study. Otherwise, they must discontinue HRT to allow confirmation of post-menopausal status prior to study enrolment. For most forms of HRT, at least 2-4 weeks should elapse between the cessation of therapy and the blood draw; this interval depends on the type and dosage of HRT. Following confirmation of their post-menopausal status, they can resume use of HRT during the study without use of a contraceptive method.

Based on the absence of an identified reproductive hazard from preclinical studies, absence of a genotoxic potential, and very low levels of mepolizumab that might be present in semen, there is no recognized risk for mepolizumab to affect human sperm or the foetus if transferred to a female partner via semen. Therefore, the use of condoms or other methods of contraception in the male study subject is not required.

12.4. Appendix 4 – Definition of and Procedures for Recording, Evaluating, Follow-Up and Reporting of Adverse Events

12.4.1. Definition of Adverse Events

Adverse Event Definition:

- An AE is any untoward medical occurrence in a patient or clinical investigation subject, temporally associated with the use of a medicinal product, whether or not considered related to the medicinal product.
- NOTE: An AE can therefore be any unfavourable and unintended sign (including an abnormal laboratory finding), symptom, or disease (new or exacerbated) temporally associated with the use of a medicinal product.

Events meeting AE definition include:

- Any abnormal laboratory test results (haematology, clinical chemistry, or urinalysis) or other safety assessments (e.g., ECGs, radiological scans, vital signs measurements), including those that worsen from baseline, and felt to be clinically significant in the medical and scientific judgement of the investigator.
- Exacerbation of a chronic or intermittent pre-existing condition including either an increase in frequency and/or intensity of the condition.
- New conditions detected or diagnosed after study treatment administration even though it may have been present prior to the start of the study.
- Signs, symptoms, or the clinical sequelae of a suspected interaction.
- Signs, symptoms, or the clinical sequelae of a suspected overdose of either study treatment or a concomitant medication (overdose per se will not be reported as an AE/SAE unless this is an intentional overdose taken with possible suicidal/self-harming intent. This should be reported regardless of sequelae).
- “Lack of efficacy” or “failure of expected pharmacological action” per se will not be reported as an AE or SAE. However, the signs and symptoms and/or clinical sequelae resulting from lack of efficacy will be reported if they fulfil the definition of an AE or SAE.

Events NOT meeting definition of an AE include:

- Any clinically significant abnormal laboratory findings or other abnormal safety assessments which are associated with the underlying disease, unless judged by the investigator to be more severe than expected for the subject’s condition.
- The disease/disorder being studied or expected progression, signs, or symptoms of the disease/disorder being studied, unless more severe than expected for the subject’s condition.

- Medical or surgical procedure (e.g., endoscopy, appendectomy): the condition that leads to the procedure is an AE.
- Situations where an untoward medical occurrence did not occur (social and/or convenience admission to a hospital).
- Anticipated day-to-day fluctuations of pre-existing disease(s) or condition(s) present or detected at the start of the study that do not worsen.

12.4.2. Definition of Serious Adverse Events

If an event is not an AE per definition above, then it cannot be an SAE even if serious conditions are met (e.g., hospitalization for signs/symptoms of the disease under study, death due to progression of disease, etc).

Serious Adverse Event (SAE) is defined as any untoward medical occurrence that, at any dose:

a. Results in death

b. Is life-threatening

NOTE:

The term 'life-threatening' in the definition of 'serious' refers to an event in which the subject was at risk of death at the time of the event. It does not refer to an event, which hypothetically might have caused death, if it were more severe.

c. Requires hospitalization or prolongation of existing hospitalization

NOTE:

- In general, hospitalization signifies that the subject has been detained (usually involving at least an overnight stay) at the hospital or emergency ward for observation and/or treatment that would not have been appropriate in the physician's office or out-patient setting. Complications that occur during hospitalization are AEs. If a complication prolongs hospitalization or fulfils any other serious criteria, the event is serious. When in doubt as to whether "hospitalization" occurred or was necessary, the AE should be considered serious.
- Hospitalization for elective treatment of a pre-existing condition that did not worsen from baseline is not considered an AE.

d. Results in disability/incapacity

NOTE:

- The term disability means a substantial disruption of a person's ability to conduct normal life functions.
- This definition is not intended to include experiences of relatively minor medical significance such as uncomplicated headache, nausea, vomiting, diarrhoea, influenza,

and accidental trauma (e.g. sprained ankle) which may interfere or prevent everyday life functions but do not constitute a substantial disruption
e. Is a congenital anomaly/birth defect
f. Other situations:

 Medical or scientific judgment should be exercised in deciding whether reporting is appropriate in other situations, such as important medical events that may not be immediately life-threatening or result in death or hospitalization but may jeopardize the subject or may require medical or surgical intervention to prevent one of the other outcomes listed in the above definition. These should also be considered serious. Examples of such events are invasive or malignant cancers, intensive treatment in an emergency room or at home for allergic bronchospasm, blood dyscrasias or convulsions that do not result in hospitalization, or development of drug dependency or drug abuse
g. Is associated with liver injury and impaired liver function defined as:

 ALT \geq 3xULN and total bilirubin[*] \geq 2xULN (>35% direct), or ALT \geq 3xULN and INR^{**} $>$ 1.5. 
* Serum bilirubin fractionation should be performed if testing is available; if unavailable, measure urinary bilirubin via dipstick. If fractionation is unavailable and ALT \geq 3xULN and total bilirubin \geq 2xULN, then the event is still to be reported as an SAE.
 
** INR testing not required per protocol and the threshold value does not apply to subjects receiving anticoagulants. If INR measurement is obtained, the value is to be recorded on the SAE form.

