7.3.1.4. Cardiovascular and Death Events

Investigators will be required to fill out the specific CV event page of the CRF for the cardiovascular Aes and SAEs, as listed in Appendix 4: Section 12.4.3.

In addition, all deaths will require a specific death data collection tool to be completed. The death data collection tool includes questions regarding cardiovascular (including sudden cardiac death) and non-cardiovascular death.

This information should be recorded within one week of when the death is first reported.

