Serious and Other Significant Adverse Events					
3.10.	Safety	AE1	Summary of Pre-Treatment Serious Adverse Events by System Organ Class and Preferred Term	
 
MEA116841
 
201607For studies with few events/participants listing is sufficient: discuss this option with your disclosure representative.
 
MEA116841 + 201607
 
	IA , SAC

Safety: Tables					
No.	Population	IDSL / Example Shell	Title	Programming Notes	Deliverable [Priority]
3.11.	Safety	AE1	Summary of On-Treatment Serious Adverse Events by System Organ Class and Preferred Term	
 
MEA116841
 
201607For studies with few events/participants listing is sufficient: discuss this option with your disclosure representative.
 
MEA116841 + 201607
 
	IA , SAC
3.12.	Safety	AE1	Summary of Post-Treatment Serious Adverse Events by System Organ Class and Preferred Term	
 
MEA116841
 
201607For studies with few events/participants listing is sufficient: discuss this option with your disclosure representative.
 
MEA116841 + 201607
 
	IA , SAC
3.13.	Safety	AE16	Summary of Serious Adverse Events by System Organ Class and Preferred Term (Number of Participants and Occurrences)	Required for data disclosure 
 
MEA116841
 
201607For studies with few events/participants listing is sufficient: discuss this option with your disclosure representative.
 
MEA116841 + 201607
 
	IA , SAC

Safety: Tables					
No.	Population	IDSL / Example Shell	Title	Programming Notes	Deliverable [Priority]
3.14.	Safety	AE1	Summary of On-Treatment Non-Fatal Serious Adverse Events by System Organ Class and Preferred Term	
 
MEA116841
 
201607For studies with few events/participants listing is sufficient: discuss this option with your disclosure representative.
 
MEA116841 + 201607
 
	IA , SAC
3.15.	Safety	AE1	Summary of Fatal Serious Adverse Events by System Organ Class and Preferred Term	
 
MEA116841
 
201607For studies with few events/participants listing is sufficient: discuss this option with your disclosure representative.
 
MEA116841 + 201607
 
	IA , SAC

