3.16.	Safety	AE1	Summary of Drug-Related Non-Fatal Serious Adverse Events by System Organ Class and Preferred Term	
 
MEA116841
 
201607For studies with few events/participants listing is sufficient: discuss this option with your disclosure representative.
 
MEA116841 + 201607
 
	IA , SAC

Safety: Tables					
No.	Population	IDSL / Example Shell	Title	Programming Notes	Deliverable [Priority]
3.17.	Safety	AE1	Summary of Drug-Related Fatal Adverse Events by System Organ Class and Preferred Term	
 
MEA116841
 
201607For studies with few events/participants listing is sufficient: discuss this option with your disclosure representative.
 
MEA116841 + 201607
 
	IA , SAC
3.18.	Safety	AE3	Summary of Non-Serious Drug-Related Adverse Events by Overall Frequency	
Required for Plain Language Summary
 
 
MEA116841
 
201607For studies with few events/participants listing is sufficient: discuss this option with your disclosure representative.
 
MEA116841 + 201607
 
	IA , SAC
3.19.	Safety	AE3	Summary of Serious Drug-Related Adverse Events by Overall Frequency	
Required for Plain Language Summary
 
 
MEA116841
 
201607For studies with few events/participants listing is sufficient: discuss this option with your disclosure representative.
 
MEA116841 + 201607
 
	IA , SAC

Safety: Tables					
No.	Population	IDSL / Example Shell	Title	Programming Notes	Deliverable [Priority]
3.20.	Safety	mid_mepo_egpa_lap /interim1 Table 3.16	Summary of All Cardiovascular Events Reported by the Investigator	
 
MEA116841
 
201607 For studies with few events/participants listing is sufficient: discuss this option with your disclosure representative.
 
MEA116841 + 201607
 
	IA , SAC
Adverse Events of Special Interest					
3.21.	Safety	mid_mepo_egpa_lap /interim1 Table 3.17	Summary of On-Treatment Adverse Events of Special Interest: Systemic Reactions	
 
MEA116841
 
201607
 
	IA , SAC

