## CONFIDENTIAL

MEA116841

ICH: Listings					
No.	Population	IDSL / Example Shell	Title	Programming Notes	Deliverable [Priority]
Exposure and Treatment Compliance					
9.	Safety	See mid_mepo_egpa_lap/interim1 Listing 10	Listing of Exposure Data		IA , SAC
10.	Safety	See mid_mepo_egpa_lap/interim1 Listing 26	Listing of Current and Previous Treatment		IA , SAC
Adverse Events					
11.	Safety	AE8	Listing of All Adverse Events		IA , SAC
12.	Safety	AE7	Listing of Subject Numbers for Individual Adverse Events		IA , SAC
13.	Safety	AE2	Listing of Relationship Between Adverse Event System Organ Classes, Preferred Terms, and Verbatim Text		IA , SAC
Serious and Other Significant Adverse Events					
14.	Safety	AE8	Listing of Fatal Serious Adverse Events		IA , SAC
15.	Safety	AE8	Listing of Non-Fatal Serious Adverse Events		IA , SAC
16.	Safety	AE14	Listing of Reasons for Considering as a Serious Adverse Event		IA , SAC
17.	Safety	AE8	Listing of Adverse Events Leading to Withdrawal from Study / Permanent Discontinuation of Study Treatment		IA , SAC
18.	Safety	See mid_mepo_egpa_lap/interim1 Listing 19	Listing of Adverse Events Defined by the Investigator as a Systemic (Non-Allergic or Allergic/Hypersensitivity) Injection Reaction		IA , SAC

ICH: Listings					
No.	Population	IDSL / Example Shell	Title	Programming Notes	Deliverable [Priority]
19.	Safety	See mid_mepo_egpa_lap/interim1 Listing 20	Listing of Adverse Events Defined by the Investigator as a Local Injection Site Reaction		IA , SAC
20.	Safety	See mid_mepo_egpa_lap/interim1 Listing 21	Listing of AEs of Systemic Reactions Meeting Anaphylaxis Criteria		IA , SAC
21.	Safety	See mid_mepo_egpa_lap/interim1 Listing 22	Listing of Potential Opportunistic Infections		IA , SAC
22.	Safety	See mid_mepo_egpa_lap/interim1 Listing 23	Listing of Serious Ischemic AEs		IA , SAC
23.	Safety	See mid_mepo_egpa_lap/interim1 Listing 24	Listing of Malignancies		IA , SAC
Corticosteroid Medication					
24.	Safety	See mid_mepo_egpa_lap/interim1 Listing 11	Listing of Corticosteroid Therapy		IA , SAC

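### No planned display is defined on all deaths, so a zero in the fatal-SAE table cannot be read as no deaths; SAEs in never-dosed subjects also lack the display that SAP 7.1 implies

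*Protocol*

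**What the plan says.** Four parts of the plan meet here.

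- **AE definition (Protocol 12.4.1).** Among the events that are not AEs it lists: "The disease/disorder being studied or expected progression, signs, or symptoms of the disease/disorder being studied, unless more severe than expected for" the subject's condition.
- **SAE definition (Protocol 12.4.2).** It opens with: "If an event is not an AE per definition above, then it cannot be an SAE even if serious conditions are met". One of the examples in brackets is "death due to progression of disease".
- **Death collection (Protocol 7.3.1.4).** Here there is no AE condition: "all deaths will require a specific death data collection tool to be completed". On content: "The death data collection tool includes questions regarding cardiovascular (including sudden cardiac death) and non-cardiovascular death".
- **Planned displays (SAP 9.7.5 and 9.7.6).** Three displays are dedicated to fatal events: Table 3.15, "Summary of Fatal Serious Adverse Events by System Organ Class and Preferred Term"; Table 3.17, "Summary of Drug-Related Fatal Adverse Events by System Organ Class and Preferred Term"; and Listing 14, "Listing of Fatal Serious Adverse Events". All three use the Safety population.

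On a separate matter, SAP 7.1 says that SAEs in screen failures, run-in failures and enrolled but untreated subjects are to be classed as pre-treatment SAEs. SAP 4 defines the Safety population as subjects with at least one dose.

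**The concern.** The protocol collects every death, but the SAP reports fatal events only through AE and SAE records. Between the two lies the death that an investigator judges to be the expected course of EGPA. It goes on the death tool and cannot enter a fatal-event display. What those displays show then depends partly on an open-label investigator's view of whether the fatal course was expected.

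This matters for three reasons. Protocol 9.1 gives informing the risk-benefit assessment in EGPA as the purpose of interim analyses, and SAP 3.1 records that one was used for regulatory submissions. Protocol 10.7 names all-cause mortality, with cardiovascular safety, as the primary focus of the independent monitoring committee, which serves only until the parent trial is complete. And Protocol 2.2 lists the heart among the organs EGPA can affect, so a cardiac death could be attributed to the disease. The tool's cardiovascular versus non-cardiovascular question bears directly on such a death.

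For never-dosed subjects the stake is smaller: SAP 7.1 sets a classification rule that the display list does not carry out.

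**Working it through.** No event count, hypothesis or sample size is involved, so the check is a reading of the definitions against the display list.

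**Step 1: can a death fall outside the SAE definition?** Protocol 12.4.1 excludes expected progression from AEs. Protocol 12.4.2 says a non-AE cannot be an SAE whatever its seriousness, and names death from progression as a case. Death is the first seriousness criterion in that section, but it applies only to events that are already AEs. So yes, provided the course is judged no more severe than expected.

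**Step 2: is that death still recorded?** Yes. Protocol 7.3.1.4 asks for the tool for all deaths.

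**Step 3: where could it be displayed?**

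| Displays | Basis | Can hold a non-AE death? |
|---|---|---|
| Tables 3.15, 3.17; Listing 14 | Fatal SAEs or drug-related fatal AEs | No |
| Table 3.20 | Investigator-reported cardiovascular events; Protocol 7.3.1.4 and 12.4.3 ask for that CRF page for AEs and SAEs | Not by the stated route |
| Tables 3.31-3.33, 3.40-3.41 | On-treatment AEs of special interest | No |
| Tables 1.1-1.2; Listings 2-3 | Disposition, withdrawal, discontinuation | Possibly; categories not given |

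Count of planned displays: 13 study population tables + 49 safety tables + 24 listings = 86. Titles that name death or the death tool: 0. Displays dedicated to fatal events: 3, all AE- or SAE-based. The derivations in SAP 9.4 define no death variable.

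**Step 4: SAEs in never-dosed subjects.** Protocol 7.3.1.1 records SAEs related to participation or to a sponsor product from consent, so such an SAE can exist before any dose. SAP 7.1 calls it pre-treatment. Table 3.10 (pre-treatment SAEs) and Listings 14-16 (fatal SAEs, non-fatal SAEs, reasons for seriousness) are all on Safety. Nobody is both never dosed and in Safety, so these displays cannot contain the event. Five displays use All Subjects Enrolled (Tables 1.3, 1.5 and 1.7; Listings 1 and 2), and none is an AE or SAE display.

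**The case against.** The strongest reply is that the route is very narrow. Protocol 12.4.1 counts an exacerbation of a pre-existing condition as an AE, and likewise a course more severe than expected. Subjects also have their benefit:risk reassessed before each dose. Few deaths would pass through as merely expected. This stands and limits the size of the point, but it does not remove it, because Protocol 12.4.2 names this very case.

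A reader might infer that such a death would vanish from the report. The documents do not support that. Tables 1.1-1.2 and Listings 2-3 use sponsor shells that are not reproduced and may include death as a reason. They are not, however, shown to give cause of death or SAE status.

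A reader might also say that Table 3.15 undercounts. It does not: it counts fatal SAEs, as its title says. The gap is that no other display is defined on all deaths.

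It can be added that cardiovascular displays are planned, that the Safety Review Team looks at open-label safety data, and that post-mortem findings go to the sponsor. The cardiovascular displays rest on AE/SAE reporting, so they do not help with a death that is not an AE. The other two are oversight and collection, not reported output. The daily review in Protocol 4.1 is of SAEs.

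Finally, the programme exists to supply drug, has no endpoints or hypotheses, and only summarises data. That is true and means no inference is at risk. It still leaves the safety summary as the main product of the SAP.

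On never-dosed subjects, SAP 1.1 mentions only one screen or run-in failure, and no affected SAE is documented. Table 3.10 still works for dosed subjects with an SAE before the first dose.

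**Conclusion.** The point holds in limited form and is worth correcting. As the display list stands, a zero in Table 3.15 cannot be read as no deaths, because a death judged to be expected EGPA progression is collected but has no display defined to receive it. The documents give no death count, so the number affected is unknown and may be zero. They do not show that any death has been missed, or that one would be absent from the whole report.

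The separate point also holds: Table 3.10 and Listings 14-16 cannot contain the never-dosed SAEs that SAP 7.1 classes as pre-treatment. Its practical scope appears small.

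The conclusion rests on display titles, populations and notes, since the shells are not in the documents. It applies to MEA116841. The guidance document for 201607 is not supplied, so whether that programme collects all deaths cannot be checked.

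**What to change.** 1. Add to the SAP, for MEA116841, one all-cause death summary (Safety population) and one listing (All Subjects Enrolled), both taken from the death data collection tool regardless of SAE status. Show cause as recorded (cardiovascular, including sudden cardiac death, or non-cardiovascular), whether the death was also reported as an SAE, and days from last dose if the tool captures date of death. The documents describe only the tool's cause questions, so that last item must be confirmed.
2. Footnote that events in former subjects are not actively sought (Protocol 7.3.1.1). Show 201607 deaths only as reported, since SAP 7 says that programme was not monitored.
3. Run Table 3.10 and Listings 14-16 on All Subjects Enrolled, or add one listing of SAEs in never-dosed subjects. SAP 7 already allows a population other than Safety where specified.

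The cost is one table, one or two listings and, if the first option in item 3 is taken, changed population labels. The protocol already requires the death tool, so it needs no amendment.
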